Specific Aim3: Determine the relationship between markers of DNL, liver fat accumulation and serum concentrations of lipids, uric acid and liver function markers before and after the fructose challenge

- We will measure serum concentrations of liver function markers, lipids and uric acid at week 0 and week 3;
- As in previous aims, data will be analyzed using students T test, and Pearsons correlations.

Subject Population	Inclusion Criteria
key criteria for Inclusion and Exclusion:	
 Subjects between 12 and 40 years No history of alcohol abuse (> 7 drinks per week) History of fructose intake of < 14 drinks per week Caucasian ethnicity BMI > 25kg/m² – 32kg/m² or 85th -99th percentile but otherwise healthy
	Exclusion Criteria
	
 ages < 12 and > 40 years Pregnant/lactating known alcohol abuse or fructose intake > 14 drinks per week not of Caucasian ethnicity glucose levels > 100 mg/dl if fasting, > 140mg/dl if within 2 hours post meal and > 200 mg/dl if random sample taking anti-hypertensive, anti-diabetic, uric acid and/or lipid-lowering medications known diagnosis of diabetes, fructose intolerance, chronic kidney disease, NAFLD or any liver-related disease, hypertriglyceridemia, polycystic ovary syndrome, hypothyroidism, obstructive sleep apnea, hypopituitarism and hypogandism BMI < 25kg/m² or > 32 kg/m² or < 85th or > 99th percentile Liver fat fraction >5% as per baseline MRI scan
Number Of Subjects	200 for first phase and 48 for the second and third phases
Study Duration	The first phase will be about 30 minutes and the second and third phase will be divided into two visits. Both visits in both phases will be about 3.5 hours each.
Study Phases	(1) Screening: We will screen participants for eligibility to participate in the study based on the inclusionary/exclusionary criteria specified above. The 200 children and young adults selected to participate will provide saliva which will be used to extract DNA and then genotype 10 SNPs. These SNPs are selected based on their association with de novo lipogenesis (DNL) or liver fat accumulation in previously published studies in Caucasians. We will select 12 children and 12 young adults with more than 15 risk alleles and 12 children and 12 young adults with less than six number of risk alleles.
Screening	
Study Treatment	
Follow-Up	

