Safety Evaluations	
At screening, to check for blood glucose values, we will conduct a spot glucose check using a glucometer (Accu-Chek, Roche Diagnostics, CH) to check that the glucose levels of the participants are in the normal range (fasting < 100mg/dl, post meal < 140 mg/dl and random < 200 mg/dl). Secondly, we will have a physician who will be available if needed. We will also conduct pregnancy test if needed.
 
Also, we will exclude participants for further participation if we find that the participant has high liver fat fraction (>5%) during our baseline MRI scan¹⁰. The participant will be given a report that they can show to their physician for treatment.

Statistical And Analytic Plan	Our main outcome measure is change in liver fat via MRI scan, fatty liver index equation and through fibroscan measurements. We will also measure serum concentrations of other lipids, liver function markers and uric acid. Data will be assessed using descriptive measures and confidence intervals. Paired t-tests and repeated measures regression analysis will be performed to explore the significant differences between week 0 and week 3.
DATA AND SAFETY MONITORING PLAN	A data and safety monitoring plan will be instituted for this study that will ensure adherence to the protocol approved by UNC IRB. [name] (PI) and co-investigators will review the phenotype and genotype data as they are generated. Any adverse event that is reported to either the principal investigator or her designated research associates by the subject or medical staff caring for the subject and which meets the criteria will be documented as such. Any event that is reported will then generate an adverse event report, which will be submitted to the IRB. The report will include a description of the event, when and how it was reported, as well as any official chart records or documentation to corroborate the event or the reporting of the event

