2 STUDY OBJECTIVE

2.1 Our goal for this study is to generate preliminary data that is needed to support an application to NIH for funding of a larger, adequately-powered study to explore whether a set of genotypes, that increase the risk for nonalcoholic fatty liver disease (NAFLD), predispose individuals to increased *de novo* lipogenesis (DNL) and liver fat accumulation when exposed to fructose intake.

2.2 Primary Objective: To explore the genetic-specific effects of fructose on liver fat accumulation using MRI

2.3 Secondary Objective: To explore the genetic-specific effects of fructose on markers of liver fat accumulation (fibroscan⁵ and fatty liver index⁶) and serum biomarkers related to lipids, uric acid and liver function.

3 INVESTIGATIONAL PLAN (brief overview)

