We will conduct a spot glucose check using a glucometer (Accu-Chek, Roche Diagnostics, CH) to check that the glucose levels of the participants are in the normal range (fasting < 100mg/dl, post meal < 140 mg/dl and random < 200 mg/dl). The exclusion criteria includes ages < 12 and > 40 years, known alcohol abuse or fructose intake > 14 drinks per week, not of Caucasian ethnicity, glucose levels > 100 mg/dl if fasting, > 140mg/dl if within 2 hours post meal and > 200 mg/dl if random, and known diagnosis of diabetes, fructose intolerance and chronic kidney disease.

We will collect saliva from the eligible 200 children and young adults, extract DNA and genotype 10 SNPs shown in Table1.

Genotyping: SNPs will be genotyped from DNA extracted from saliva. Genotyping will be conducted in [name] lab using TaqManSNP genotyping assays (Applied Biosystems, Foster City, CA). The minor allele frequencies (MAFs) of these SNPs range between 7 and 49% based on Caucasian ethnic background. Therefore we are confident about finding 48 individuals with all 10 SNPs. If we don't find individuals with the 10 SNPs, we will mine the literature and find more SNPs that have a role in liver lipogenesis.

4.2

Intervention/Treatment procedures (by visits)

Phase2: Selection of 48 participants for the acute fructose challenge and 3-week intervention study:

The risk allele will be defined as the allele that is associated with higher levels of liver lipogenesis or fat as per previously published studies in Caucasians. The number of risk alleles will range from 0 to 20. The SNP will get a score of 2 with two risk alleles, 1 with one risk allele and 0 with no risk alleles. All the score will be added to get a cumulative score between 0 and 20 for 10 SNPs. We will select participants having > 15 risk alleles and < 6 risk alleles for our acute challenge and 3-week intervention study.

Phase 2&3- visit 1- MRI scan: The 48 individuals enrolled will visit the UNC NRI clinical suite run by the Human Research Core. After obtaining consent, they will be taken to the WakeForest Imaging center for baseline MRI scan. Studies have shown that 5-6% of liver fat is considered normal and anything more than that can reflect increased risk for fatty liver. If the MRI report of the participants shows liver fat > 6%, we will consult with the participant (if > 18years) and/or their parents in confidence and explain why they (or their child) cannot continue to

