- Medical History: Information related to medical conditions, procedures and surgeries
- Modifiable activity form: Information related to physical activity, sedentary time and job activities
- Medications: Information related to prescription, non-prescription and traditional medications
- Dietary data: Combination of diet recall and food frequency questionnaire will be used to obtain detailed dietary data.

Sample preparation: A total of 24 mL of blood will be drawn at fasting at baseline, 1 hour, 3 hours, at weeks 0 and 3 by a trained phlebotomist through venous puncture. After centrifugation, the serum and plasma fractions of the blood samples will be aliquoted and stored at -80°C to measure the biomarkers listed below using standard reference procedures. All samples will be labeled and inventoried as per standard protocols. Urine will be collected at the same points as blood samples collected at baseline, 3 hour at weeks 0 and 3 will be stored at -80°C. The Human Research Core will assist with phlebotomy services

Meals: All participants will be provided standardized meal for the evening prior to participation of part 1 of phase 2.

Assessment of liver fat accumulation and stiffness: Magnetic resonance imaging (MRI): We will assess liver fat accumulation at week 0 and week 3 using the 2012 Siemens MAGNETOM Skyra 3T MRI system available at the WakeForest Translational Imaging program. If the liver fat fraction >5%¹⁰ then we will exclude the participant from further participation in the nutrient challenge.

Transient elastography: We will use transient elastography to ascertain the changes in the amount of fat in the liver. Transient elastography using a **Fibroscan®** is a non-invasive method of assessing fat accumulation in liver and liver stiffness and works on the principle of vibration controlled transient elastography⁵. A vibration of mild amplitude and low frequency is transmitted through the intercostal space using a vibrator at the skin surface. The vibration induces an elastic shear that propagates through the hepatic tissue. Using pulse echo ultrasound acquisition, the velocity of the shear wave can be determined. The shear wave, directly related to tissue stiffness and expressed in kilopascal (kPa), can be a helpful aid to clinically manage patients with liver disease. The UNC Human Research Core houses a Fibroscan and its trained technicians will help with its use for this study.

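### Groups formed on liver-fat alleles are then screened on baseline liver fat, so the high-versus-low contrast may not represent the genetic effect in all people at high or low risk; the direction depends on an unknown correlation

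*Combined protocol and SAP*

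**What the plan says.** **Grouping.** The synopsis (Study Phases) chooses the 10 SNPs for their link to de novo lipogenesis or liver fat "in previously published studies in Caucasians". Section 4.2 fixes the direction of scoring: "The risk allele will be defined as the allele that is associated with higher levels of liver lipogenesis or fat". The two ends of this score form the groups, 24 people in each.

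**Exclusion.** The baseline MRI follows group selection. The synopsis excludes "Liver fat fraction >5% as per baseline MRI scan", and section 3.4 repeats the 5% limit. Under liver-fat assessment, section 4.2 says of anyone above 5%: "then we will exclude the participant from further participation in the nutrient challenge". The visit 1 text of the same section uses another figure for people who cannot continue: "If the MRI report of the participants shows liver fat > 6" (per cent). The synopsis also excludes known diagnoses, among them "chronic kidney disease, NAFLD or any liver-related disease".

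**Claim and analysis.** Objective 2.2 is "To explore the genetic-specific effects of fructose on liver fat accumulation using MRI". The synopsis objective speaks of adolescents and young adults at high and low genetic risk. Neither is limited to people with low liver fat. The between-group test is an unpaired t test (synopsis, Study Design). Section 6.3 names no adjustment for baseline liver fat or its predictors; the only covariate named anywhere is concomitant medication (4.5). No text plans to report exclusions by risk group, and 4.8 (screen failures) is empty.

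**The concern.** The limit acts on a trait that the grouping variable is presumed to raise. If the premise is right, a high-risk person needs more offsetting traits (diet, activity, fat distribution, other genes) to pass than a low-risk person does. Groups that were comparable before the scan may therefore differ afterwards in non-genetic susceptibility. The t test cannot detect this, and the confidence interval does not reflect it.

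Section 6.4 intends these data for sizing larger studies. A systematic shift in the risk-group difference would carry into that calculation. This is a different matter from regression to the mean in the paired week 0 to week 3 comparison.

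**Working it through.** The plan gives no figure to reproduce: 48 participants are stated without alpha, effect size, SD or a rule for replacing people excluded at the scan.

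**Inputs**
- Share of those scanned who are excluded: 20-25%, averaged over two equal groups. This is a proxy, taken from the NAFLD prevalence that the synopsis cites for US adults and young adults. Overweight entrants could exceed it; removing known NAFLD and related conditions could lower it.
- s, the difference between groups in mean log liver fat, in SD: 0.5 to 1.0, assumed.
- r, the within-group correlation of baseline liver fat with 3-week change: 0.3 to 0.7, with 0 and -0.3 as checks, assumed.

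**Formulas.** Log liver fat is normal with equal SD in both groups. With limits z_L (low risk) and z_H = z_L - s (high risk), the share excluded is 1 - Phi(z). The mean residual among those who pass is m(z) = -phi(z)/Phi(z). The shift in the high-minus-low contrast is r × [m(z_H) - m(z_L)], in SD of response before selection.

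**Example.** For a 20% average and s = 0.5, z_L = 1.118 and z_H = 0.618. Then 13.2% of the low-risk and 26.8% of the high-risk group are excluded. The residual means are -0.246 and -0.450, a difference of -0.204. At r = 0.5 the shift is 0.5 × (-0.204) = -0.102 SD.

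| Average excluded | s | Low | High | Residual difference | r=0.3 | r=0.5 | r=0.7 | r=-0.3 |
|---|---|---|---|---|---|---|---|---|
| 20% | 0.5 | 13.2% | 26.8% | -0.204 | -0.061 | -0.102 | -0.143 | +0.061 |
| 20% | 0.8 | 9.5% | 30.5% | -0.317 | -0.095 | -0.159 | -0.222 | +0.095 |
| 20% | 1.0 | 7.4% | 32.6% | -0.385 | -0.115 | -0.192 | -0.269 | +0.115 |
| 25% | 0.5 | 17.2% | 32.8% | -0.229 | -0.069 | -0.115 | -0.161 | +0.069 |
| 25% | 0.8 | 12.9% | 37.1% | -0.358 | -0.108 | -0.179 | -0.251 | +0.108 |
| 25% | 1.0 | 10.3% | 39.7% | -0.438 | -0.131 | -0.219 | -0.307 | +0.131 |

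At r = 0 every shift is zero. With a weaker score effect, s = 0.2 to 0.3, the shift at r = 0.5 is only -0.04 to -0.07 SD.

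**Scale.** With 24 per group the standard error of the contrast is sqrt(2/24) = 0.29 SD. The difference detectable with 80% power at an assumed two-sided 0.05 is (1.96 + 0.84) × 0.29 = 0.81 SD.

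**Planning.** Required sample size varies as 1/effect². If a true difference of 0.50 SD were estimated as 0.40 SD (a shift of -0.10), the planned size would rise by (0.50/0.40)² = 1.56. This holds the response SD fixed; truncation also narrows that SD, which offsets part of the loss.

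**The case against.** The limit is a declared entry criterion, applied equally to both groups and justified in 1.3 as reducing risk. Objectives need not restate eligibility, so part of this is simply a narrower target population. The study is exploratory, and 6.4 concedes that it may lack power. Every shift at r = 0.5 is below one standard error. If the larger study keeps the same limit, the pilot contrast applies to that population. The design already balances age group, restricts BMI and caps sugary drinks, so adjustment may add little.

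Much of this stands. It lowers the size of the point and confines the remedy to claims, one extra analysis and reporting. It does not remove the point. Among people who pass, the groups may still differ in non-genetic determinants, so restricting the population does not by itself make the contrast a genetic effect. A shift below one standard error is still systematic when the estimate is used for planning.

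Three stronger readings are tempting, and the documents do not support them.
- A reader might infer that the limit necessarily biases toward no genetic effect. That needs a positive r, which no text gives. Measurement error in the baseline scan pushes the correlation with change in the negative direction.
- A reader might apply the cited 20% to the low-risk group alone. At s = 0.5, 0.8 and 1.0 that excludes 37%, 48% and 56% of the high-risk group, with shifts of -0.12, -0.21 and -0.28 SD at r = 0.5. The averages it implies, 28%, 34% and 38%, exceed the cited all-genotype figures.
- A reader might infer that a null result will be reported as no genetic effect. The plan nowhere says so.

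**Conclusion.** The structure is established by the documents: grouping on liver-fat alleles, later exclusion on liver fat, objectives without that restriction, and an unadjusted between-group test. That more high-risk than low-risk people would be removed follows from the protocol's premise, but the documents do not quantify it. Direction and size are conditional. The bias is toward the null only if baseline liver fat and response are positively correlated. Under the stated assumptions at r = 0.5 it is about -0.10 to -0.22 SD, which is modest beside the precision of 24 per group but relevant to planning. The 5% and 6% limits give different exclusion shares, so the size cannot be settled until they agree. The change should be made, because it alters what the pilot can conclude at very little cost.

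**What to change.** Leave the exclusion in place.

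1. In 2.2 and 6.4, limit the risk-group contrast to people at or under the baseline liver-fat limit. State that selection may bias it, toward the null if baseline fat and response are positively related. Do not call it conservative without that condition.
2. In 6.3, add a sensitivity analysis of the risk-group difference in liver-fat change, adjusted for predictors already collected: age group, BMI or waist, body fat and habitual sugar intake. Say that it removes only the measured part of the selection.
3. Retain the baseline MRI value of everyone scanned, including those excluded. Report baseline liver fat and the proportion excluded by risk group, with a confidence interval. The pilot then estimates the differential exclusion for use in planning the larger study.
4. Reconcile the 5% limit (synopsis, 3.4, and liver-fat assessment in 4.2) with the 6% in the visit 1 text of 4.2.

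The cost is wording, one added model and retention of scans already taken, with no extra visits. The claim becomes narrower.

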Dietary factors spur the development of NAFLD: Unhealthy diet plays a major role in the development of NAFLD. Most of the attention has been on increased calorie intake. However, an important but underappreciated dietary change in US society for the past few decades has been increase in fructose intake. Contained in soft drinks, fruit juices and energy drinks, fructose affects many metabolic processes, foremost being an increase in fat accumulation in liver and contributing to the onset and progression of NAFLD (**Figure 1**). Fructose, which is almost entirely metabolized in liver, is rapidly phosphorylated to fructose 1 phosphate by fructokinase (ketohexokinase) with ATP depletion in parallel. The fructose 1 phosphate gets metabolized to dihydroxyacetone-phosphate and glyceraldehyde and finally to triglycerides¹⁵⁻¹⁷ which gets deposited in liver and leads to NAFLD.

Fructose is a more potent stimulator of DNL than glucose: In population studies, it has been shown that fructose, and not glucose, is associated with increased visceral adiposity, insulin resistance and hyperuricemia¹⁸⁻²⁰. Fructose is unique in its effects that it stimulates KHK and thus potentiates its own metabolism. Secondly, the rate of phosphorylation of fructose by KHK is 10 times higher than the phosphorylation of glucose by glucokinase. Third, fructose is directly absorbed into portal vein and delivered to liver without entering the systemic circulation. Liver, thus, is exposed to a much higher fructose load than rest of the tissues. Fourth, fructose activates the lipogenic transcriptional factors, SREBP1c and ChREBP in the liver, promoting DNL²¹. And finally, fructose tends to deplete liver ATP levels and one of the outcomes is generation of more AMP which get converted to uric acid. Uric acid has been shown to stimulate fat synthesis in the hepatocyte thus pointing to an additional pathway through which fructose can increase liver fat^{22,23}.

Genes and gene by nutrient interactions play a major role in the regulation of NAFLD: Both genetic and environmental factors contribute to the onset and progression of NAFLD. NAFLD is a complex and heritable phenotype. Family-based studies have reported heritability estimates for NAFLD to be between 20% and 70%^{7,8}. Genome-wide and candidate gene studies have identified several genes associated with NAFLD⁸. Representative genes that were implicated in lipid metabolism and in the development and progression of NAFLD are shown in **Table1**. Few studies have shown that fructose affects lipogenesis in liver in a genotype-specific manner. Davis and colleagues found that Hispanic children with GG genotypes of *PNPLA3* SNP rs738409 were more inclined to accumulate fat in the liver as compared to children with CC or CG genotypes³. Similarly, another study investigating the effects of added sugars on liver fat found that individuals with TT of rs1260326 of *GCKR* increased their *de novo* lipogenesis by 44% during an oral fructose + glucose challenge⁴. However, none of the studies have shown the cumulative effects of SNPs on change in liver fat when exposed to fructose.

The genetic-specific effects of fructose on liver lipogenesis need to be studied as a first step towards individualized nutrition: This study assumes significance given that fructose affects liver lipogenesis differentially based on genotypes. It also paves the way towards individualized or personalized nutrition. Previous studies investigating the metabolic effects of fructose have been controversial. Some have shown significant effects of fructose on insulin sensitivity and *de novo* lipogenesis and triglycerides while others have shown no effects²³⁻²⁷. The range of these studies is wide, with the duration of the intervention ranging from 7 to 665 days, sample size ranging between 8 and 64 per group and amount of fructose per day ranging from 40 to 250g/d. For this exploratory and feasibility study we have selected the duration of 21 days, sample size as 12 per group and amount of fructose a ~0.75g/kg/day (equivalent to two sodas/per day).

1.1 Introduction

This study is a combination of acute and long-term investigation of the effects of fructose on liver lipogenesis and whether genetics modify this relationship. It is similar to a case-control study based on the number of alleles that increase the risk for liver lipogenesis which further increases the risk for NAFLD. There is an increasing concern about the effects of fructose on metabolic diseases. Some studies, as shown in the background section, have also suggested that effects of fructose may be modified by some genotypes. However, all these studies have focused on only one gene or genotype. We fill the gap by conducting the study with a set of genotypes.

1.2 Name and Description of Investigational Product or Intervention

Acute fructose challenge: We will be using a fructose drink which will be prepared by dissolving 0.75g/kg fructose + 0.45g/kg glucose (NOW Foods, Bloomingdale IL), in 24oz water. This composition of fructose and glucose mimics the composition of fructose and glucose in 2 regular sodas²⁸ based on an approximate adolescent/adult body weight of ~65kg.

3-week intervention: We will provide each participant the same drink as described in the acute fructose challenge to be taken one per day.

